All primary analyses will be performed using intent-to-treat principles. All variables will first be assessed for evidence of outlier values or skewed distributions. Baseline characteristics and potential confounders will be summarized for participants randomized to Group 1 versus Group 2 using standard methods such as means/standard deviations and medians/inter-quartile ranges for continuous variables and frequencies with percentages for categorical variables. Differences between the groups at baseline will be statistically tested using t-tests for continuous variables or non-parametric alternatives as indicated and Chi-square tests for categorical variables. Any differences detected will be adjusted for in multivariable models. Our primary analytic approach will be mixed effects linear regression which will enable efficient estimation of treatment effects, inclusion of all study participants in intent-to-treat analyses, and the same analytic approach to be used for all three Aims. Analyses will focus on differences in outcomes when participating in PLIE vs. UC. Fixed effects terms will be included for treatment (PLIE vs. UC), sequence (Group 1 vs. Group 2), time (baseline, 4 months, 8 months) and the interaction between treatment*time. Subjects will be modeled as random effects. Models also will adjust for any baseline differences in demographic factors or confounders that may occur due to chance. Covariates will be included to adjust for any co-interventions that occur (e.g., medication changes), and sensitivity analyses will be performed excluding participants who experience co-interventions. Standard diagnostic tests will be performed to examine model assumptions and distributions of residual values and to assess for potential leverage and influence points. To minimize the risk of Type I error due to multiple comparisons with co-primary outcomes, we will adjust p-values using bootstrapping (SAS Proc Multtest).

12.4 If this study has undergone scientific or scholarly review, please indicate which entity performed the review:

- Cancer Center Protocol Review Committee (PRC) (Full approval is required prior to final CHR approval for cancer-related protocols.)
- CTSI Clinical Research Center (CRC) advisory committee
- Departmental scientific review
- Other:

Specify **Other**:

Department of Veterans Affairs; SFVA R&D Committee

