13.0 Background

13.1 Background:

Dementia is common in older Veterans, affecting nearly 1 in 10 of those age 65 years or older (~1 million individuals), and prevalence is expected to rise as Korean and Vietnam-era Veterans grow older. Currently available dementia medications are associated with small improvements in cognitive and physical function (standardized effect sizes, 0.11-0.33) but have many adverse effects and do not stop or slow the disease course.¹⁻³ In addition, several new medications that initially appeared promising have recently failed in Phase III clinical trials.⁴⁻⁸ In contrast, there is growing evidence that behavioral interventions such as physical, mental and social activity are beneficial in individuals with dementia and have minimal adverse effects.⁹⁻¹¹ We have recently developed a novel, integrative exercise program called Preventing Loss of Independence through Exercise (PLIÉ) that focuses on training procedural memory (unconscious learning of procedures, which is relatively well-preserved in individuals with dementia) to build the strength and capacity to perform the movements that are most needed for daily function (e.g., standing up from sitting) while also increasing mindful body awareness and facilitating social connection.^{12,13} **The objective of this study is to perform a randomized, controlled trial to test the efficacy of PLIÉ for improving function and quality of life and reducing caregiver burden in individuals living in the community with dementia.**

13.2 Preliminary studies:

We performed a pilot-test of PLIÉ at an adult day health center in San Francisco, CA.^{12,13} Study participants were 12 individuals with mild to moderate dementia attending an adult day health program in San Francisco, CA, and their primary caregivers. Participants in the PLIÉ group (n=7) attended the program for 45 minutes, 2 to 3 days/week (depending on their daily attendance at the center) for 18 weeks while participants in the Usual Care (UC) group (n=5) engaged in standard chair-based exercises at the center. Outcomes were assessed at baseline and 18 weeks and included standard measures of cognitive function (Alzheimer's Disease Assessment Scale – cognitive subscale, ADAS-cog), physical performance (Short Physical Performance Battery, SPPB), quality of life (Quality of Life Scale in Alzheimer's Disease, QOL-AD); and caregiver burden (Caregiver Burden Inventory, CBI).

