We propose to enroll 120 dyads of individuals with dementia and their primary caregivers, with a goal of 20 dyads per intervention site. Veterans with dementia who are current clients at the site will be prioritized for enrollment. If we are unable to enroll our target sample of 20 Veterans with dementia at a given site, enrollment will be opened to non-Veterans with dementia at the site as well as Veterans and non-Veterans with dementia who are not currently clients at the site but are living in the community near the site and willing to attend for the study. Caregivers are not required to be Veterans, but their participation is necessary because they are providing care to the primary participants, many of whom will be Veterans.

Inclusion criteria, primary participant:

- diagnosis of memory loss or dementia
- mild to moderate severity (defined as Clinical Dementia Rating of 0.5, 1, or 2)
- English language fluency
- attendance or willingness to attend adult day health center at least 2 days/week on days that PLIE will be offered

Inclusion criteria, caregivers:

- Provide care for primary participant
- Able to answer study questionnaires related to participant's functional status, dementia-related behaviors, quality of life and their own feelings about caregiving
- English language fluency

14.7 Exclusion criteria:

Exclusion criteria, primary participant:

- Plans to change days of attendance during the study period so that participant would no longer be attending on at least 2 PLIE days/week
- Planning to leave the facility during the study period and not willing to come for PLIE classes at least 2 days/week
- Severe vision or hearing impairment (e.g., unable to see or hear well enough to follow instructions)
- Several physical impairment (e.g., paralysis or hemi-paralysis; wheel-chair or bed bound)
- Severe mental health condition (e.g., uncontrolled depression, PTSD, bipolar disorder)
- Limited life expectancy (e.g., enrolled in or eligible for hospice; metastatic cancer)
- Started dementia medication (cholinesterase inhibitor or memantine) in past 3 months
- Planning to change dementia medication during the study period
- Current participation in another research study
- Lack of legal supporting documentation for HIPAA (e.g., durable power of attorney, court ordered legal guardianship, advance health directives), If determined to lack capacity to consent.
- Lack of consent/assent to study procedures

Exclusion criteria, caregivers:

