Schedule of Evaluations. The table below provides an overview of study procedures and the schedule of evaluations. Briefly, screening will be performed by telephone and will include assessment of demographics and eligibility criteria. The consent visit will be performed in person with the participant and legally authorized representative (LAR) together; detailed consent procedures are provided in the Informed Consent section. After consent has been obtained, global cognitive function will be assessed in participants. The LAR may serve as the study caregiver or may designate someone else (e.g., other family member, paid caregiver) to play this role. The baseline, 4-month and 8-month visits will be performed with the participant and caregiver separately and will include measurement of participant and caregiver outcomes and potential confounders and mediators. Adverse events and co-interventions (e.g., medication changes) will be assessed during monthly caregiver check-ins during the intervention period. Each visit is described in more detail below. All of these research-related activities will be performed by our research team. Staff at the study sites will NOT be engaged in research and will be responsible for referring potential participants to our research team for screening; escorting study participants to and from the exercise intervention space; assisting study participants who need to use the toilet; and providing space for our exercise instructors to deliver the intervention.

Overview of Study Procedures and Schedule of Evaluations

	Screening	Consent	Baseline	4 Months	8 Months	Monthly CG Check-ins
Eligibility	X					
Demographics/ medical history	X					
Capacity to Consent		X				
Informed Consent		X				
Global cognitive function		X				

Outcomes			X	X	X	
Confounders/ mediators	nnn	nnn	X	X	X	
Adverse events						X
Co-Interventions						X

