- Cognitive function (Alzheimer’s Disease Assessment Scale – Cognitive Subscale, ADAS-cog). Cognitive function will be measured using the Alzheimer’s Disease Assessment Scale – cognitive subscale (ADAS-cog). The ADAS-cog is one of the most commonly used outcome measures in dementia drug treatment trials and is one of the measures considered by the Food and Drug Administration for approval of dementia medications. It includes direct assessment of learning (10-word list), naming (objects), following commands, constructional praxis (figure copying), ideational praxis (mailing a letter), orientation (person, time, place), recognition memory and remembering test instructions and is scored on an 80-point scale with higher scores reflecting worse cognitive function. Prior studies have found the ADAS-cog to be valid and reliable with Cronbach’s alpha greater than 0.8 and test-retest reliability above 0.9.

- Physical performance (Short Physical Performance Battery (SPPB)). The SPPB was developed by the National Institute on Aging to provide an objective tool for measuring physical performance in older adults. **Lower body strength** is assessed based on time to complete 5 chair stands without using arms. **Balance** is assessed based on the ability to hold different stands for 10 seconds, including the side-by-side, semi-tandem and full tandem stands. **Mobility** is assessed based on usual walking speed over a 3-meter walking course. The **total SPPB score** is the sum of the 3 component scores and may range from 0 to 12. Prior studies have found that the SPPB is valid and reliable and associated with important outcomes including disability and mortality. A recent systematic review concluded that the SPPB was one of the best tools available to measure physical performance in older adults based on reliability, validity and responsiveness.

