Randomization. Study participants will be enrolled in one study site at a time in blocks of 20, and the randomization sequence will be generated in advance in blocks of 20 (10 Group 1, 10 Group 2) using a random number generator on a computer. The sequence will be stored in a secure location accessible only to intervention staff, and research staff who enroll study participants and collect outcome data will be unaware of the randomization sequence.

Blinding. Because we are using a waitlist design with usual care as the control condition, it will not be possible to blind study participants or their caregivers. However, research staff who collect outcome data will be blinded to group assignment. Every effort will be made to ensure that blinding is maintained including: 1) having interviewers remind study caregivers not to discuss any aspect of the study or ask any questions related to the study prior to scheduling or performing assessments; 2) excluding interviewers from staff meetings that discuss details of the intervention; and 3) maintaining the group assignment list separately from other study documentation. Interviewers also will be asked to guess which group participants were in to assess the adequacy of the blinding procedures.

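### The only mixed model described adjusts for post-randomisation co-interventions with coding left open, so its treatment coefficient need not be the intent-to-treat effect

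*Combined protocol and SAP*

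**What the plan says.** Section 12.3 opens with the principle: "All primary analyses will be performed using intent-to-treat principles". It then describes one mixed effects linear regression for all three aims, with fixed effects for treatment, sequence, time and treatment by time, and a random subject effect. Two sentences later comes "Covariates will be included to adjust for any co-interventions that occur (e.g., medication changes"), and in the same sentence "sensitivity analyses will be performed excluding participants who experience co-interventions". The section gives no version of the model without the co-intervention covariates and no other sensitivity analysis. It does not say which events qualify or how the covariate is coded.

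Section 16.1 shows where the data come from: "Adverse events and co-interventions (e.g., medication changes) will be assessed during monthly caregiver check-ins during the intervention period". Its paragraph on adherence, adverse events and co-interventions lists changes in medications, caregivers, medical conditions, usual activities and other factors, collected on a standardised questionnaire. The blinding paragraph says that "it will not be possible to blind study participants or their caregivers". Section 14.7 excludes anyone "Planning to change dementia medication during the study period", so the dementia-medication changes that remain are unplanned ones.

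**The concern.** All randomised participants stay in the model, so the issue is not lost participants. It is that the model conditions on events occurring after randomisation. Assignment may influence such events directly, or indirectly if PLIÉ slows decline and decline prompts a change of medication. If the events are also tied to the outcome, comparing participants with the same co-intervention history is no longer the randomised comparison.

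Two things follow. First, the reported coefficient for the co-primary outcomes can differ from the effect of assignment by an amount that depends on a coding choice the plan leaves open. Second, the planned sensitivity analysis selects on the same events, so it is not an intent-to-treat check on the adjusted model.

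Usual activities are the clearest possible route. Section 16.1 aims to hold PLIÉ classes at the same time as usual exercises, so if a change in usual activities is coded as a co-intervention, assignment itself can produce it.

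**Working it through.** **1. The plan's own figure.** Inputs from section 14.4: SPPB effect size 0.34, correlation 0.75, alpha 0.03 (two-sided reproduces the table), one pre and two post measures.

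- Variance factor for mean post minus pre: (1 + 0.75)/2 + 1 - 2 × 0.75 = 0.375.
- n per group = 2 × (2.170 + 0.842)² × 0.375 / 0.34² = 58.9, so 59, as stated.
- Power computes to 0.808 at 60 per group and 0.709 at 48 per group (stated 0.81 and 0.71).

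No co-intervention term enters, so removing those covariates changes none of these figures.

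**2. What the month-4 effect is.** The fixed effects fill all six group-by-visit means. The month-4 effect is therefore the Group 1 change from baseline minus the Group 2 change. One change has variance 2 × (1 - 0.75) = 0.5 (SD 0.707). At 60 per group the standard error is sqrt(2 × 0.5/60) = 0.129 SD.

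A person-level ever/never covariate is constant within a person. With complete data it leaves this within-person contrast alone (change below 0.0001 SD in simulation).

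**3. Assumptions.** The documents give no event rates or dependences. The stated model was simulated with 600,000 subjects per scenario, correlation 0.75, and the effect maintained in Group 1. The usual-care event rate is 10% or 25% per four months. Event log-odds rise with decline by 0.5, 1 or 2 per SD of scored change. The covariate is time-varying (preceding interval or cumulative).

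In the last column events follow the true state, and 0.10 of the 0.25 within-person variance is taken as measurement error. That split is an assumption, prompted by the ADAS-cog "test-retest reliability above 0.9" quoted in section 16.1.

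**4. True effect 0.34 SD, co-intervention itself without effect.**

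| Rate | Slope | Adjusted estimate | With measurement error |
|---|---|---|---|
| 10% | 0.5 | 0.335 | 0.337 |
| 10% | 1 | 0.324 | 0.330 |
| 10% | 2 | 0.304 | 0.315 |
| 25% | 0.5 | 0.33 | 0.333 |
| 25% | 1 | 0.31 | 0.32 |
| 25% | 2 | 0.27-0.28 | 0.29 |

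Largest shift: 0.34 - 0.27 = 0.07 SD, and 0.07/0.129 = 0.54 standard errors.

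**5. No true effect.** Decline-driven events alone give no bias (0.0003 SD at 25%). If assignment also shifts event log-odds by 0.7 either way, the adjusted estimate lies between about -0.05 and +0.065 SD (about -0.04 to +0.05 with measurement error). Conversely, with a true effect of 0.34 SD and events shifted by assignment but unrelated to outcome, the bias is 0.0001 SD.

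**6. The co-intervention itself helps.** Section 13.1 supplies a range: "Currently available dementia medications are associated with small improvements in cognitive and physical function (standardized effect sizes, 0.11-0.33"). Using 0.11 or 0.33 SD with a true direct effect, adjusted minus intent-to-treat is -0.058 to +0.008 SD.

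With no direct PLIÉ effect, events unrelated to decline, a 25% usual-care rate and 0.33 SD benefit, a 0.7 log-odds shift moves the PLIÉ event rate to 14.2% or 40.2%. The effect of assignment is then 0.33 × (0.142 - 0.25) = -0.036 or 0.33 × (0.402 - 0.25) = +0.050 SD. The adjusted model returns about -0.01 or +0.02 (preceding-interval coding) or 0 (cumulative).

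**7. Exclusion analysis.** In the step 4 scenarios it drops 15-41% of participants, and its estimate falls as low as 0.22 SD. At the 25% rate its shift is -0.062 against -0.030 for the covariate model at slope 1, and -0.123 against -0.064 at slope 2: same direction, about twice as far.

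**The case against.** The strongest reply is that the plan may be harmless as written. Section 12.3 lists the core fixed effects without co-interventions, the covariate sentence does not contain the word primary, and a person-level indicator would leave the month-4 contrast unbiased with complete data. This stands in part. A reader might infer that every stated analysis is biased; the documents do not support that, because they leave the coding open. Adjustment of the primary model is still the natural reading, since no other model is described.

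A reader might also infer that decline-driven events are enough to bias the result. They are not: events must depend on both assignment and outcome, and the null-case shifts need an assumed doubling or halving of event odds that no passage supports.

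Nor do the documents establish that usual-activity changes will be covariates. The usual-care paragraph of section 16.1 gives those data an exploratory use, and the only example in section 12.3 is medication changes. Use in the main model is not ruled out, because the same paragraph also says the data serve to detect co-interventions or contamination.

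It would also go too far to call the two planned analyses uninformative side by side. The exclusion analysis moves about twice as far in the decline-driven cases, so a gap between them carries some signal, though a small one against the standard error.

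Finally, the size is modest. At slopes of 0.5 to 1 the loss in step 4 is at most about 0.03 SD, under a quarter of a standard error, and towards no effect. The half-standard-error figure there needs a slope of 2, an odds ratio of about 7.4 per SD of change.

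**Conclusion.** The concern holds in a conditional form. The plan promises an intent-to-treat estimate, but the only model it describes conditions on post-randomisation events with unspecified coding, and its only sensitivity analysis selects on the same events. With a time-varying covariate, and events related to both assignment and outcome, the coefficient need not be the effect of assignment. If either relation is absent there is no bias; nor is there under person-level coding for the month-4 contrast with complete data.

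All sizes rest on assumed rates, slopes and shifts. Within them the covariate bias reaches about half a standard error. For scale, section 13.2 treats 0.25 SD as clinically meaningful, and the steepest 25% scenario takes 0.34 SD most of the way there. Agreement between the adjusted and exclusion analyses would be weak reassurance. This should be fixed but is not fatal to the trial.

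**What to change.** In section 12.3, name the mixed model without co-intervention covariates as the primary analysis. Tabulate co-interventions by group and period, so that any imbalance is visible. Keep the adjusted and exclusion analyses as supplementary, labelled as not estimating the intent-to-treat effect. State in advance which events qualify, including whether usual-activity changes count, and whether the covariate is coded by preceding interval, cumulatively or per person.

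The cost is SAP wording only. No new data are needed, and the planned 120 participants and stated power do not change.

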13.0 Background

13.1 Background:

Dementia is common in older Veterans, affecting nearly 1 in 10 of those age 65 years or older (~1 million individuals), and prevalence is expected to rise as Korean and Vietnam-era Veterans grow older. Currently available dementia medications are associated with small improvements in cognitive and physical function (standardized effect sizes, 0.11-0.33) but have many adverse effects and do not stop or slow the disease course.¹⁻³ In addition, several new medications that initially appeared promising have recently failed in Phase III clinical trials.⁴⁻⁸ In contrast, there is growing evidence that behavioral interventions such as physical, mental and social activity are beneficial in individuals with dementia and have minimal adverse effects.⁹⁻¹¹ We have recently developed a novel, integrative exercise program called Preventing Loss of Independence through Exercise (PLIÉ) that focuses on training procedural memory (unconscious learning of procedures, which is relatively well-preserved in individuals with dementia) to build the strength and capacity to perform the movements that are most needed for daily function (e.g., standing up from sitting) while also increasing mindful body awareness and facilitating social connection.^{12,13} **The objective of this study is to perform a randomized, controlled trial to test the efficacy of PLIÉ for improving function and quality of life and reducing caregiver burden in individuals living in the community with dementia.**

13.2 Preliminary studies:

We performed a pilot-test of PLIÉ at an adult day health center in San Francisco, CA.^{12,13} Study participants were 12 individuals with mild to moderate dementia attending an adult day health program in San Francisco, CA, and their primary caregivers. Participants in the PLIÉ group (n=7) attended the program for 45 minutes, 2 to 3 days/week (depending on their daily attendance at the center) for 18 weeks while participants in the Usual Care (UC) group (n=5) engaged in standard chair-based exercises at the center. Outcomes were assessed at baseline and 18 weeks and included standard measures of cognitive function (Alzheimer's Disease Assessment Scale – cognitive subscale, ADAS-cog), physical performance (Short Physical Performance Battery, SPPB), quality of life (Quality of Life Scale in Alzheimer's Disease, QOL-AD); and caregiver burden (Caregiver Burden Inventory, CBI).

Feasibility was assessed based on enrollment and retention. A total of 22 individuals were invited to participate in the study; of these, 8 declined (primarily due to lack of time/interest), 2 withdrew prior to the baseline assessment and 12 (55%) enrolled. Of the 12 who enrolled, 1 (PLIÉ) withdrew prior to the 18-week assessment (92% completion rate).

Effect sizes were estimated based on the mean standardized difference between PLIÉ and UC from baseline to 18 weeks (i.e., mean change from baseline to 18 weeks in PLIÉ group minus mean change from baseline to 18 weeks in UC group divided by the baseline standard deviation [SD] in both groups combined). We observed evidence of clinically meaningful between-group differences (≥ 0.25 SDs) for measures of cognitive function (ADAS-cog), physical performance (SPPB), quality of life (QOL-AD, participant and caregiver) and caregiver burden (CBI). **These effect sizes are substantially larger than has been observed with current dementia medications and affect a broader range of outcomes than current behavioral interventions.** These pilot data demonstrate convincingly that: 1) we can work successfully with community-based adult day health centers; 2) we can enroll and retain individuals with dementia and their caregivers in an integrative exercise intervention study; 3) we can successfully deliver the PLIÉ program to individuals with mild to moderate dementia; and 4) a larger study of the PLIÉ program is highly likely to find significant improvements in physical performance, cognitive function and quality of life and reduction in caregiver burden relative to usual care.

18-Week Change and Effect Size (ES) Calculations from PLIÉ Pilot Trial				
Measure	PLIÉ	UC	Baseline SD	Standardized ES†
Participant Measures				
Cognitive function (ADAS-cog)*	-4.6	2.4	9.2	+0.76
Physical performance (SPPB)	1.0	0.2	2.4	+0.34
Quality of life (QOL-AD)	6.0	2.6	4.1	+0.83
Caregiver Measures				
Participant quality of life (QOL-AD)	2.2	0.0	7.2	+0.33
Caregiver burden (CBI)*	-5.5	1.8	14.2	+0.49

* lower scores reflect better performance. † + values reflect better outcomes with PLIÉ; values ≥ 0.25 considered clinically meaningful.

13.3 References:

